2.5 SAMPLE SIZE CALCULATIONS

This study is powered to detect at least 7 percentage points or greater in handwashing rates between treatment and control schools. The minimum detectable effect size (MDES) of 7 percentage points was determined as a policy-relevant benchmark based on IDinsight's conversations with our partner, UNICEF, about school-based handwashing campaigns in the Philippines. In our previous study, handwashing rates in Philippines schools were estimated at around 2 percent. As in our previous studies, a scale-up recommendation to DepEd will require that the program demonstrate improvements to handwashing that move rates beyond the threshold of 15 percent. Therefore, assuming conservatively that the baseline control group handwashing rates among the schools in our sample is 10 percent and the intra-cluster correlation is 0.1^{27} , a sample size of 100 schools in total with MDES of 7 pp provides sufficient power to inform the policy decision above with some buffer.

²² Ibid.

²³ Ram, Pavani K., et al. "Is structured observation a valid technique to measure handwashing behavior? Use of acceleration sensors embedded in soap to assess reactivity to structured observation." *The American journal of tropical medicine and hygiene* 83.5 (2010): 1070-1076.

²⁴ Ibid.

²⁵ Halder, Amal K., et al. "Observed hand cleanliness and other measures of handwashing behavior in rural Bangladesh." BMC Public Health 10.1 (2010): 545.

²⁶ Ram, Pavani. "Practical guidance for measuring handwashing behavior: 2013 update." Water & Sanitation Program: Working Paper (2013).

²⁷ ICC=0.07 from previous HiFive study. We use an ICC of 0.1 as a more conservative estimate, in the event that handwashing outcomes are more correlated within schools in ZDN compared to the provinces (Puerto Princesa and Camarines del Norte) where our previous HiFive took place.

Pre-analysis plan [DRAFT] | January 20, 2020

Provided the true effect of the program is indeed as small as 7 percentage points, a sample size of at least 100 schools with 26 handwashing observations per school enables the experiment to be well-powered, or sensitive enough, to detect a difference of this magnitude or greater with an 80 percent chance of statistical significance.

To buffer against attrition due to safety risks (i.e. not being able to observe a school because the area is deemed unsafe), we expanded the sample size to 132 in total, with 66 schools per arm.

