Unit	Co-variate	Metric	Hypothesized relationship to outcome
	District Number of pupils enrolled (pre- intervention)	 X.1 – categorical variable where each value category represents the school district where the school is located X.2 – continuous variable to represent the number of pupils enrolled at the elementary school prior to intervention³⁷ X.3 – index variable between 0 and 11 	 School district is associated with geographic location, which may be associated with varying levels of rurality, access to water, socio-economic status of teachers and pupils, or support received from DepEd division office. Given that school budget is partially determined by number of pupils enrolled, and that larger schools tend to be located in urban or semi-urban areas, school resources and the school pupil and teacher population may vary depending on school size. This will be estimated using information reported by principals during end-line school visits or using the data reported in DepEd's Online Monitoring System (OMS), depending on how reliably information reported by principals can be collected.
School	WinS implementatio n quality index score (pre- intervention)	composed of 11 binary indicators related to WASH conditions at the school, as reported in OMS data by principals prior to the intervention ³⁸	Higher score indicates a higher level of reported quality of WinS implementation, and may thus be associated with a higher level of handwashing infrastructure and supplies, as well as more consistent implementation of WinS program activities involving pupils, such as group handwashing and tooth- brushing.
	Nudge- enabled	X.4–binary variable for whether school is "nudge-enabled" or not "nudge-enabled"	Nudge-enabled schools are those with combinations of features that indicate they may be more conducive to nudge intervention than schools without those features. Please see Section 2.5 Recruitment of Participants (Sampling) for details of these nudge-enabling features. Because of the presence of these features, the nudge intervention may have greater impact on nudge-enabled schools than schools that are not.

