 $^{^{\}rm 39}$ Observations in which the student grade was unknown will be excluded.

Pre-analysis plan [DRAFT] | January 20, 2020

1.d.iv. Treatment impact by WinS implementation quality index score: In order to compare the average effect of the nudges intervention on the outcome of independent handwashing after toilet use across different levels of WinS implementation quality, sub-group analysis will be conducted using the following regression:

$$Y_{ij} = \beta_0 + \beta_1 T_j + \beta_2 W_j + \beta_3 (T_j \times W_j) + \overrightarrow{\beta_4} \overrightarrow{X}_{4ij} + \varepsilon_{ij}$$

Where:

- *W_j* is an ordinal variable between 0 and 11 denoting the WinS implementation quality index score for school *j*
- \vec{X}_{4ij} represents a vector of pupil, school, and class level co-variates as specified in Table 2, excluding WinS implementation quality index score
- All other regression terms are defined as they were in the previous regression specification and β₃ is the coefficient of interest.

1.d.v. Treatment impact by nudge conduciveness: In order to compare the average effect of the nudges intervention on the outcome of independent handwashing after toilet use depending on the context's conduciveness to nudges, sub-group analysis will be conducted using the following regression:

Where:

$$Y_{ij} = \beta_0 + \beta_1 T_j + \beta_2 W_j + \beta_3 (T_j \times N_i) + \beta_4 X_{4ij} + \varepsilon_{ij}$$

- N_i will be a binary variable (to be constructed after seeing the distribution) =1 if the pupil
 was exposed to a nudge-conducive handwashing environment at the time of toiet use and
 =0 if not
- \vec{X}_{4ij} represents a vector of pupil, school, and class level co-variates as specified in Table 2, excluding WinS implementation quality index score
- All other regression terms are defined as they were in the previous regression specification and β₃ is the coefficient of interest.

1.e. Presentation of results: a regression table will be included for each specification to describe the correlation between key indicators of interest and co-variates. Data visualizations describing the level of the outcomes variables in the treatment and control group may also be included.

RESEARCH QUESTION 2

2.a Research question 2: What is the causal impact of the behavioral nudge intervention on pupil access to handwashing facilities with soap and water?

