Table 6 below summarize the outcomes described for each research question above, and indicates the number of hypotheses being tested with each "family" of outcomes. The analysis will correct p-values based on the number of hypotheses being tested for each family of outcomes.

⁴¹ Abdi, Hervé. "Holm's sequential Bonferroni procedure." Encyclopedia of research design 1, no. 8 (2010): 1-8.

Research Question	Outcome Group	Indicator Type	Indicator	Sample	Number of hypotheses tested within each family of outcomes for p-value correction
1	Independent	Main	Independent HWWS after toilet use	All grades	n/a because main effect
	Handwashing With Water and Soap After	Main	Independent HWWS after toilet use among grades 1-3	Grades 1-3	
	Toilet Use	Main	Independent HWWS after toilet use among grades 4-6	Grades 4-6	
		Sub-group	Gender	All grades	4
			Wins implementation quality	All grades	
			Number of pupils	All grades	
			Nudge conduciveness of handwashing area	All grades	
	Independent Handwashing With At Least Water After Toilet Use	Main	Independent HW with water after toilet use	All grades	n/a because main effect
2	Availability of Handwashing	Main	Availability of functioning handwashing facilities with soap	All HW facilities	4
	Facilities		Availability of functioning handwashing facilities	All HW facilities	
			Presence of functional handwashing facility with soap near toilet facility	All HW facilities	
			Presence of functional handwashing facility near toilet facility	All HW facilities	
	Availability of Toilets	Main	Functioning toilet per pupil	All schools	n/a because separate outcome family

Table 6: Number of Hypotheses Tested For Each Family of Outcomes

LIMITATIONS AND CORRECTIONS TO THE ANALYSIS

Outliers and Missing Values: Missing values can take the form of non-response (e.g. uncompleted surveys), partial response (e.g. "Don't know" responses), or errors in the data. Minimal missing data is expected since the digital survey forms include constraints that require data to be entered before the enumerator can proceed with data collection. If co-variates have missing values for some observations, a dummy variable will be generated and included in the analytic model, and missing values for co-variates will be replaced with 0⁴².

Cross-tabulations: cross-tabulations of variables may be conducted to provide additional insights on the relationship between variables within the sample of schools surveyed.

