Additional Hypothesis Testing: Additional analyses may be conducted following the conclusion of data collection if additional questions of interest arise. Any analyses that are not specified in this pre-analysis plan will be indicated and justified as such.

⁴² Alternatively, and depending on the number missing values across co-variates, multiple imputation may be used to account for missing values in the analysis.

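### The missing co-variate rule makes no exception for sub-group moderators, so any unknown moderator value would bias the interaction coefficient in that sub-group model

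*SAP*

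**What the plan says.** - **The rule.** SAP Section 6, Outliers and Missing Values: when a co-variate is missing, "a dummy variable will be generated and included in the analytic model, and missing values for co-variates will be replaced with" 0. Footnote 42 gives the alternative: "depending on the number missing values across co-variates, multiple imputation may be used to account for missing values in the analysis". It names no threshold for switching and no imputation model.
- **What counts as a co-variate.** Table 4 lists enrolment (X.2), WinS score (X.3), pupils present in the class (X.5), nudge conduciveness (X.6) and pupil gender (X.7, female = 1).
- **The moderators.** Section 1.d under Research Question 1 names four: gender, WinS score, number of pupils and conduciveness. Each is a Table 4 variable. Equations are written for all but number of pupils, with β3 on the treatment-by-moderator product as the coefficient of interest. None has a treatment-by-missing term.
- **The one moderator with its own rule.** Footnote 39, attached to the grade-group comparison: "Observations in which the student grade was unknown will be excluded".
- **How much missing data is foreseen.** Little, because the forms force entry. The same paragraph nevertheless counts don't-know answers as missing. For enrolment, Table 4 chooses between principals' reports and the OMS, "depending on how reliably information reported by principals can be collected".

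**The concern.** For a baseline co-variate used only for adjustment in a randomised comparison, zero plus a dummy is a common and mostly harmless device: the dummy absorbs whatever the arbitrary zero does to the outcome level. That does not carry over to a variable that multiplies treatment. The dummy corrects the level of the unknown group but not its treatment effect, so the unknowns' effect is credited to whichever moderator value 0 stands for. For gender that is boys, for X.6 non-conducive areas, and for class size a class with no pupils, which lies far outside the real range.

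At stake is β3. Section 4 relies on modelling heterogeneity by environment to handle clutter, and Annex C ties a gender difference to redesign of the nudges. A β3 distorted by coding could hide a real difference or suggest one that does not exist.

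**Working it through.** **1. The plan's own figure.** The SAP gives no figure for missing moderators or interaction tests. Its sample size (Section 2.5) sets the scale of the study: "This study is powered to detect at least 7 percentage points or greater in handwashing rates between treatment and control schools"; "the baseline control group handwashing rates among the schools in our sample is 10 percent"; "the intra-cluster correlation is 0.1"; 26 observations per school; "with an 80 percent chance of statistical significance". With two-sided alpha 0.05 (sidedness is not stated):

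- n per arm = [1.96·√(2·0.135·0.865) + 0.842·√(0.10·0.90 + 0.17·0.83)]² / 0.07² ≈ 373.
- Design effect = 1 + 25·0.1 = 3.5, and 373·3.5/26 = 50.2 schools per arm.
- Power at 50 per arm is 0.798 (pooled variance) or 0.801 (unpooled), so the stated 100 schools is reproduced.

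**2. Binary moderator.** Let m be the share missing at random and half the pupils girls (assumed). The group coded 0 holds true boys, (1−m)/2, and all unknowns, m, half of whom are girls. The share of the true interaction kept is

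1 − 0.5m / [(1−m)/2 + m] = 1/(1+m).

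Conduciveness behaves the same way if half the areas are conducive.

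**3. Continuous moderator.** Z is the zero-filled moderator and b the true slope of the treatment effect:

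- Cov(effect, Z) = (1−m)·b·sd²
- Var(Z) = (1−m)·sd² + m(1−m)·mean²
- Share kept = sd² / (sd² + m·mean²)

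Example, mean 30 and m = 0.05: SD 8 gives 64/(64+45) = 0.587; SD 10 gives 100/(100+45) = 0.690.

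| Missing | Gender | Class size, SD 10 | Class size, SD 8 |
|---|---|---|---|
| 1% | 0.990 | 0.917 | 0.877 |
| 2% | 0.980 | 0.847 | 0.780 |
| 5% | 0.952 | 0.690 | 0.587 |
| 10% | 0.909 | 0.526 | 0.416 |

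The SAP gives no mean, SD or missing share, so all of these are assumptions. With SD 8 and 5% missing, a mean of 25 keeps 0.672 and a mean of 35 keeps 0.511.

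**4. Simulation.** 132 schools × 26 pupils, school-clustered standard errors, 800 runs per setting, class size mean 30 and SD 10. The true interactions are assumed: 0.06 for gender and 0.0030 per pupil for class size.

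| Moderator | Missing | Mean β3, zero-fill | Power, zero-fill | Power, unknowns excluded |
|---|---|---|---|---|
| Class size | 0% | 0.0030 | 0.606 | – |
| Class size | 5% | 0.0020 | 0.419 | 0.581 |
| Class size | 10% | 0.0016 | 0.371 | 0.592 |
| Gender | 0% | 0.060 | 0.750 | – |
| Gender | 5% | 0.057 | 0.675 | 0.682 |
| Gender | 10% | 0.054 | 0.648 | 0.678 |

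Adding a treatment-by-missing-dummy term gave the same β3 as exclusion.

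**5. No true interaction, 10% missing.** With values missing at random, the mean β3 is about zero under zero-fill. If the effect is 10 points larger among the unknowns, zero-fill rejects at 0.05 in 13% of runs for gender and 36% for class size. Exclusion rejects in about 5% for both.

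**The case against.** The strongest reply is that the plan never says the rule covers moderators. It speaks of co-variates, and the gender and WinS models take the moderator out of the co-variate vector. That is a fair reading, but it leaves every moderator except grade with no missing-data rule, and zeros filled once in data preparation would still flow into the product term. Nor does the separation hold throughout: the vector in 1.d.v excludes the WinS score, so on the text X.6 stays inside it.

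Footnote 39 is also weaker evidence of inconsistency than it looks. Grade is tested by separate regressions, where a pupil of unknown grade has no sample to join.

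Several stronger readings are tempting but not supported:

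- **That footnote 42 creates the miscoding.** Multiple imputation codes nobody as a boy or as zero. It would dilute β3 only if its model left out the interaction, and no model is given.
- **That WinS scores will be missing.** Section 2.6 says each school was scored before assignment, and the score was the stratifier. The only opening is that the analysis index runs to 11 and the stratification index to 9.
- **That Table 4 shows enrolment to be missing.** It offers a second source, which makes gaps less likely.
- **That the rule always shrinks β3.** Step 5 shows otherwise.

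It also stands that class size is counted during the observation in forms that force entry, that no equation is written for number of pupils, and that footnote 37 lets enrolment become ordinal. The linear slope is therefore an assumption.

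**Conclusion.** The point holds as a minor one. The rule as written has no carve-out for moderators, and applied literally it biases β3 whenever a moderator is unknown. If values are missing at random, a real interaction is diluted; if the effect differs among the unknowns, a false interaction can arise.

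The size is nil with complete moderators, which the plan largely expects. It is small for gender, about 5% at 5% missing. It is potentially large only for a continuous number-of-pupils moderator: 59–69% of the slope kept at 5% missing, on an assumed mean of 30 and SD of 8–10. A reader might infer that sub-group losses of some 40% are to be expected. The documents do not support that, because they give no missing share and no distribution for class size.

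Only secondary sub-group tests are touched. The primary intention-to-treat estimate has no product term and is unaffected.

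**What to change.** In Section 6, Outliers and Missing Values, limit zero-plus-dummy to adjustment co-variates and add: *In each sub-group model, observations whose moderator value is unknown are excluded from that model, as is done for unknown grade.* Adding a treatment-by-missing-dummy term instead would also serve. It gives nearly the same β3, and exactly the same when no other co-variates are shared.

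In footnote 42, add that if multiple imputation is used for a moderator, the imputation model must include the treatment-by-moderator term and account for clustering by school.

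The cost is a sentence or two in a plan still marked as a draft and written before endline data collection, and a few observations lost from the affected sub-group model only.

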ANNEX C: GENDER ANALYSIS PLAN

	Table 1 Behavioral Nudges Gender Analysis Plan						
	GENDER ANALYSIS QUESTIONS What do we need to know? What are possible gender gaps? What are possible unintended consequences?	ANSWERS What are the answers to the gender analysis questions?	WHY IT MATTERS Is there a gender issue/gap that may affect grant implementation? Why does it present a barrier or opportunity for the research? How critical to the success of the research grant is it to address it?	GRANT RESPONSE Describe how the gender gap will be addressed in the design and implementation of the research grant (i.e. to close the gap, address the barrier or accelerate on the opportunity). Be specific.	MONITORING How will we monitor or measure this?		
1.	How do independent handwashing rates (with and without soap) between boys and girls compare?	Traditional gender roles tend to involve more tasks that may require hand-washing for girls than boys, such as cooking or cleaning. Thus, they may facilitate building hand-washing habits among girls, and lead girls to have a higher independent handwashing rates (with or without soap) than boys.	This is both a challenge and an opportunity for the intervention. If a gender gap in independent hand- washing is discovered, implementers can incorporate new gender- targeted measures into our intervention design. These measures can ensure that the nudges are appropriately targeting both genders.	The intervention can alter or add measures that specifically target the gender found to have lower handwashing rates. For example, if boys are found to have lower handwashing rates, implementers can put up posters designed to appeal more to boys than to girls. These measures could help close the possible gender gap in handwashing.	The evaluation will compare the handwashing rates of boys and girls in control schools, in order to determine if there is an existing gender gap in independent handwashing rates.		
2.	Will behavioral nudges based on disgust and social affiliation have greater impact on independent handwashing rates of girls than boys?	Due to gendered differences in desirable traits in children, girls may be more sensitive than boys to messages related to cleanliness and conformity. Therefore, behavioral nudges based on disgust and social affiliation	This is both a challenge and an opportunity for the intervention. As designed, the intervention may have a greater impact on girls than boys. If so, this would have the positive effect of leading to greater handwashing rates	Post designs will feature both boys and girls carrying out the same activities (handwashing alone and with peers) to ensure that there are no gendered differences in the message that they are sending. If there is a gendered difference in the impact of the intervention, and	The evaluation will compare the difference in handwashing rates between control group and treatment group by gender. That is, it will compare the nudges' impact on the		

				IDins DATA. DECISIONS.	ight development.
	GENDER ANALYSIS QUESTIONS What do we need to know? What are possible gender gaps? What are possible unintended consequences?	ANSWERS What are the answers to the gender analysis questions?	WHY IT MATTERS Is there a gender issue/gap that may affect grant implementation? Why does it present a barrier or opportunity for the research? How critical to the success of the research grant is it to address it?	GRANT RESPONSE Describe how the gender gap will be addressed in the design and implementation of the research grant (i.e. to close the gap, address the barrier or accelerate on the opportunity). Be specific.	MONITORING How will we monitor or measure this?
		may have a greater impact on handwashing rates for girls than boys.	overall, but the negative effect of creating or widening a gender gap in handwashing rates. Since nearly all of the bathrooms in our sample schools are shared by boys and girls, there is no opportunity to test different messages for boys and girls.	we suspect it is because boys and girls have different levels of sensitivity to specific emotional appeals, the intervention can be adapted to appeal equally to boys and girls in future iterations. For example, half the posters can make appeals more effective on boys, and the other half can make appeals more effective on girls.	handwashing rates of girls and of boys. This will determine if the nudges affect boys and girls in a differentiated way.
3.	Does enumerator gender affect handwashing behavior at all, or among boys and girls differentially?	It is possible that due to gendered differences in how children perceive adults, they may be more likely to wash their hands when a female enumerator is observing the classroom than a male enumerator, since they may associate female adults with reinforcing hygienic behavior. It is also possible that a female enumerator may have a greater effect on handwashing rates for girls	If there is a gendered element to how students respond to female and male enumerators, this may present a challenge for the study's observations, because it could affect the effect size observed.	To address this issue, we will do our best to hire a gender-balanced team of enumerators to conduct observation and send split male and female observers equally between treatment and control schools.	In addition to comparing the difference in handwashing rates between girls and boys, the evaluation will compare the difference between overall and gender-specific handwashing rates based on enumerator gender in control schools, to isolate the effect of enumerator gender from the nudge treatment.

33

GENDER ANALYSIS QUESTIONS What do we need to know? What are possible gender gaps? What are possible unintended consequences?	ANSWERS What are the answers to the gender analysis questions?	WHY IT MATTERS Is there a gender issue/gap that may affect grant implementation? Why does it present a barrier or opportunity for the research? How critical to the success of the research grant is it to address it?	GRANT RESPONSE Describe how the gender gap will be addressed in the design and implementation of the research grant (i.e. to close the gap, address the barrier or accelerate on the opportunity). Be specific.	MONITORING How will we monitor or measure this?
	than boys, as gender norms lead girls to perform more handwashing-related chores (cleaning).
